If the recipient does not meet the above "pre-vaccine" criteria, the recipient and donor will be taken off the study. The donor will have follow-up tests and procedures performed, as described in Section 7.0.

- 6.5 On day 0 (day of lymphocyte collection) donors will undergo a steady state pheresis to obtain lymphocytes. Donor target cell dose will be to  $\geq 2 \times 10^7$  CD3+ cells /kg recipient weight. If the target dose is not reached after 3 collections, then the donor and the recipient will be taken off the study and the apheresis product will be discarded.
  - 6.6 If successful collection, on day 0:  $1 \times 10^7$  CD3+/cells per kg will be infused into the recipient. The rest of the cells will be cryopreserved in  $5 \times 10^7$  CD3+ cells /kg recipient weight aliquot. Premedication will include only acetaminophen 650 mg po (orally) and benadryl 25 mg iv once.
- NO STEROIDS ARE TO BE GIVEN PRIOR TO LYMPHOCYTE INFUSION.
- 6.7 After DLI on same day, recipient will receive id-KLH vaccine. The vaccine will be also administered on week 4 and week 8 post DLI. The recipient will receive a total of 3 vaccines.
  - 6.8 For the donor the time of active treatment will begin the day of the first vaccine and finish 30 days after donor lymphocyte collection.
  - 6.9 For the recipient the time of active treatment will begin the day of the donor lymphocyte infusion and finish 30 days after the last vaccination.
  - 6.10 Recipients will receive GM-CSF 250 mcg/m^2 (rounded up to the nearest vial) S.C.daily for four days (days 0-3) after each vaccine. All GM-CSF injections will be given in close proximity to the vaccination, as close to the exact site of injection as possible to ensure optimal recruitment of dendritic cells. The first dose of GM-CSF will be given by a nurse, and the remaining three doses will be given by the recipient. Research staff will provide educational instructions regarding subcutaneous injection administration.
  - 6.11 Donors and/or recipients: Fever and chills associated with vaccine administration and/or GM-CSF will be treated with acetaminophen and/or meperidine. The use of non-steroidal anti-inflammatory drugs and/or steroids should be avoided.
  - 6.12 Recipients should not receive steroid premeds, or high dose steroids for other indications unless approved by the Study Chair or his designee.

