  - 6.13 Recipients failing to respond 6 months after the last vaccination can receive up to 3 subsequent doses of  $5 \times 10^7$  CD3+ cells/kg of the remaining cryopreserved cells, if no active GVHD is present. The additional lymphocyte infusions and follow up will be exactly like the first infusion.

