## **10.0 Statistical Considerations**

**Preliminaries.** This is a single-arm feasibility trial of Id Specific vaccinated DLI for treatment of multiple myeloma patients post allograft from a matched sibling donor who are not in CR or relapsing after transplant at least 3 months after stem cell transplant. The last myeloma therapy must be at least 3 weeks prior to entry. Labeling time of DLI as week 0, each donor will be vaccinated at weeks -8, -6, -2 and each patient will be vaccinated at weeks, 0, 4, and 8. Toxicity (TOX) will be defined as the event that the patient suffers grade 2, 3 or 4 GVHD or death within 6 months post DLI. The historical rate of TOX is 50% (54/107). The primary aim is to determine whether transfer of myeloma specific immunity is enhanced by vaccinating donors prior to donor lymphocyte infusion with an id-specific vaccine.

**Trial Conduct.** A maximum of 10 patients will be treated.

**Analysis of Myeloma Specific CTLs over time.** A generalized linear mixed model (Diggle, et al., 1998) will be fit to the longitudinal measurements of myeloma specific CTLs. For patient  $j = 1, \dots, 20$  at observation time  $t = -8, -6, -2, 0, 4, 8, 12$ , denote the myeloma specific CTL count by  $Y_{j,t}$  and covariate vector by  $Z_j$ . The model is given by

$$g\{E(Y_{j,t})\} = m + f_j(t) + b Z_j + \text{error}$$

where  $g$  is a suitable link function,  $m$  is the overall mean,  $f_j$  is a patient-specific function of  $t =$  time from day of DLI, accounting for the manner in which  $Y$  varies over time and includes a patient effect to account for correlation among the successive observations on each patient,  $Z_j$  is a component accounting for patient covariates with  $b$  is a covariate parameter vector, and "error" is the usual measurement of error.

Additional analyses of the final data will include analysis of survival times as functions of the treatments and patient prognostic covariates using an appropriate survival regression model determined by goodness-of-fit analyses.

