**Toxicity Monitoring Rule.** For the purpose of safety monitoring, "toxicity" will be defined as Grade 2-4 acute GVHD within 6 months of DLI. Based on an historical toxicity rate of 50%, denoting  $q = \text{Pr}(\text{toxicity})$ , it will be assumed that  $q$  follows a beta(.50, .50) prior. The trial will be stopped early for safety if  $\text{Pr}(Q > .50 | \text{data}) > .90$ . This rule will stop the trial early if  $[\# \text{ toxicities}] / [\# \text{ patients}]$  is greater than or equal to 2/2, 3/3, 4/4, 5/6, 6/7, or 7/9. The operating characteristics of this rule are as follows:

True Pr(Toxicity)	Pr(Stop Early)	Median Sample Size
.50	.35	10
.60	.52	8
.70	.70	5
.80	.88	2

**PROTOCOL COMPLIANCE** Patients will be reviewed by the study investigators who will score the patient for toxicity, and GVHD. Data must be entered in PDMS and the Study Chairman will be the final arbiter of toxicity and other outcomes should a difference of opinion exist.

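### The 6-month toxicity window, counted from the week-0 infusion, closes before any repeat infusion begins, and Section 10 does not say how GVHD after repeats enters the stopping rule

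*Combined protocol and SAP*

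**What the plan says.** **First infusion and vaccines (Section 6.0, items 6.6 and 6.7).** On day 0, 1 × 10^7 "CD3+/cells per kg will be infused into the recipient". The recipient is vaccinated the same day, and "The vaccine will be also administered on week 4 and week 8 post DLI", three vaccines in all.

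**Repeat infusions (item 6.13).** The amount per repeat is 5 × 10^7/kg. Timing and number are set by a clause that begins "Recipients failing to respond 6 months after the last vaccination can receive up to 3 subsequent doses of" that size. The cells come from the frozen remainder of the donor's collection, and GVHD must not be active at the time. The item closes by saying that "The additional lymphocyte infusions and follow up will be exactly like the first infusion".

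**Clock and toxicity event (Section 10.0).** The Preliminaries set the time axis with "Labeling time of DLI as week 0" and define TOX as the event that "the patient suffers grade 2, 3 or 4 GVHD or death within 6 months post DLI". The Toxicity Monitoring Rule states that toxicity "will be defined as Grade 2-4 acute GVHD within 6 months of DLI". It puts a beta(.50, .50) prior on the toxicity probability q and stops if the posterior probability that q exceeds .50 is above .90. Its boundaries are toxicities over patients, up to 10 patients. Section 10.0 says nothing about repeat infusions.

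**The concern.** Section 10.0 is written as if each patient has one infusion and one yes/no toxicity outcome. The treatment plan allows up to four infusions, and the later ones carry more cells each. If the 6-month window runs only from week 0, every repeat starts after it has closed.

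Limiting GVHD is central to this trial. GVHD rate is a secondary objective, Section 8.0 names GVHD as a primary clinical endpoint, and the background asks whether efficacy can be improved without more GVHD. A stopping rule that omits the larger infusions gives less assurance than its operating-characteristics table suggests. The response and GVHD rates in the secondary objectives would also mix first-infusion and retreatment outcomes, with no stated attribution.

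**Working it through.** **1. Timing.** Inputs: last recipient vaccine at week 8 (item 6.7); repeats from 6 months after it (item 6.13); window of 6 months from DLI at week 0 (Section 10.0). Six months is about 26 weeks.

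- Window closes: 0 + 26 = week 26.
- Earliest repeat after a full vaccine course: 8 + 26 = week 34.
- Gap: 34 − 26 = 8 weeks.

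If only the day-0 vaccine were given, the earliest repeat would fall at 0 + 26 = week 26, the limit of the window. GVHD after it would still be too late to count. Both definitions of toxicity in Section 10.0 use 6 months, so the timing result is the same under either.

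**2. Dose ratio.** 5 × 10^7 / 1 × 10^7 = 5.

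**3. Does the plan's table rest on one outcome per patient?** After k toxicities in n patients the posterior is Beta(0.5 + k, 0.5 + n − k). Stop when Pr(q > .50) > .90, checked after each patient. The first stopping points are 2/2, 3/3, 4/4, 4/5, 5/6, 6/7, 6/8 and 7/9. At q = .50 the stopping probability is .25 (at 2/2) + .0625 (at 4/5, = 2 × .5^5) + .027 (at 6/8) = .340.

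| True q | Stated Pr(stop) | Recomputed | Stated median N | Recomputed |
|---|---|---|---|---|
| .50 | .35 | .340 | 10 | 10 |
| .60 | .52 | .516 | 8 | 8 |
| .70 | .70 | .708 | 5 | 5 |
| .80 | .88 | .877 | 2 | 2 |

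The table reproduces to within about one percentage point with a single outcome per patient and no re-scoring. This uses the posterior criterion. The printed boundary list omits 4/5 and 6/8 and on its own gives .299/.463/.658/.847; that is a separate point.

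**4. What counting repeats could do (illustration).** The documents give neither the share retreated nor the GVHD risk after a repeat, so both are assumed. Let q1 be first-window toxicity, r the share of toxicity-free patients retreated, and q2 the risk of grade 2-4 acute GVHD among them. Per-patient toxicity over all infusions is q1 + (1 − q1) × r × q2.

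- q1 = .50, r = .50, q2 = .50: .50 + .50 × .50 × .50 = .625. Pr(stop) is .34 if repeats are not counted and .56 if they are.
- q1 = .50, low end (r = .25, q2 = .30): .50 + .50 × .25 × .30 = .5375, Pr(stop) .40.
- q1 = .50, high end (r = 1, q2 = .70): .50 + .50 × 1 × .70 = .85, Pr(stop) .94.
- q1 = .30, same ranges of r and q2: toxicity .3525 to .79. Pr(stop) is .10 if not counted and .15 to .86 if counted.

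These figures ignore the delay before late events are known.

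**5. How many patients could be affected?** In the three largest series in Table 2 response is 52%, 44% and 52%, so non-response is 48% to 56%, or about 5 of 10 patients. A patient given all three repeats would receive 3 × 5 = 15 of 16 × 10^7 cells/kg, or 94%, after the window. Both are upper bounds. The collection target in item 6.5 is at least 2 × 10^7/kg; after the first infusion a donor at that minimum leaves 2 − 1 = 1 × 10^7/kg. One repeat needs 1 + 5 = 6 × 10^7/kg collected, and three need 1 + 15 = 16 × 10^7/kg.

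**The case against.** **The rule may already cover repeats.** It says DLI, not first DLI, and item 6.13 makes follow-up after repeats match the first infusion, which could be read as opening a new 6-month window. The week-0 label also serves mainly to set out the vaccine schedule. This stands as an ambiguity. It does not close the gap: nothing says how a patient already scored would re-enter the count, and the printed table assumes that none does.

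**The events would not be missed.** A reader might infer that GVHD after repeats goes unmonitored. The documents do not support that. Section 7.0 D schedules GVHD assessments at 3, 6, 12, 18 and 24 months after the last vaccine. Treatment-related serious events stay reportable beyond 30 days. Section 9.0 lists toxicity that the study chairman deems unacceptable as a removal criterion. None of these sets a numerical threshold.

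**Not every retreated patient has been scored non-toxic.** A reader might infer this from the timing. Item 6.13 bars only GVHD that is active at retreatment. A patient whose grade 2-4 acute GVHD arose within the window and resolved may be retreated and already counts as toxic.

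**The closing sentence of item 6.13 may not be a contradiction.** A reader might see a plain conflict with the fivefold dose and the total of three vaccines. The dose is stated in the sentence just before, and the closing sentence names infusions and follow-up, not vaccines. It may mean procedure and follow-up only. The wording needs clarifying; a conflict is not established.

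**Pooling is not the only sound remedy.** Several windows per patient would be judged against a 50% benchmark that is not shown to cover repeat infusions. This is a fair argument for a separate tally.

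**Conclusion.** The point holds as a gap in the stopping rule's coverage. With DLI at week 0, repeat infusions after a full vaccine course begin about 8 weeks after the toxicity window closes, at five times the first dose per infusion, and Section 10.0 does not bring them into the count. On the natural reading, GVHD after repeats is observed but not counted; the follow-up sentence in item 6.13 leaves some doubt about intent.

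The practical size is unknown. A reader might take 5 of 10 patients, or 94% of cells, as expected values. The documents do not support that: cell supply, removal for progression requiring therapy, and active GVHD all reduce the number retreated. The stopping probabilities for pooled counting rest entirely on assumed retreatment and GVHD rates. They show that the effect on the rule could be material, not what it will be.

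The plan should be corrected, because two readers could run different stopping rules from the same text.

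**What to change.** In Section 10.0, choose and state one of two versions:

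- the 6-month toxicity window also applies after each repeat protocol infusion, with each patient counted at most once; or
- repeat infusions have a separate tally under the same posterior criterion.

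Recompute and restate the operating characteristics for the version chosen, and say how late events update counts already used. Report GVHD and response separately for the first infusion and for retreatment.

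Reconcile items 6.5 to 6.7 and 6.13 with Section 10.0: what sameness with the first infusion covers, whether the vaccine total is affected, and how the collection target relates to the cells that repeats would need. No dose or clinical rule is proposed here.

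Cost: a few sentences and one recalculated table. GVHD is already assessed, so no new procedure is needed. The real downside is that a pooled rule may stop the trial appreciably more often. Some events will also arrive 8 months or more after the first infusion, possibly after all 10 patients are enrolled, so the plan should say what a late boundary crossing means.

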## 7.0 Evaluation During Study

### A. Donor:

#### Prior to each vaccination: Within 72 Hours:

- 1) H&P, vital signs.
- 2) Albumin, total protein, calcium, glucose, BUN, creatinine, bilirubin, ALT, alkaline phosphatase, LDH, CBC with differential, PT/PTT.

- 3) Toxicity assessment after first vaccination.
- 4) Immunodeficiency panel: Quantitative immunoglobulins, and quantification of lymphocyte subsets (CD4 and CD8).
- 5) Negative serum pregnancy test if of child bearing potential if of child bearing potential.
- 6) Leukopheresis will be performed to obtain  $2 \times 10^9$  mononuclear cells (MNC) from donor and recipient.
- 7) Collect 10 cc serum and 60 cc whole blood in preservative-free heparin for idiotype-specific antibody and cellular proliferative responses once during weeks -8, -6, -4, -2, and 0.
- 8) Negative donor infectious disease panel:
  - Hepatitis B surface antigen (HBsAg)
  - Anti-Hepatitis B core antibody (HBcAb)
  - Anti-Hepatitis C Virus antibody (HCV Ab)
  - Anti-Human Immunodeficiency Virus (HIV) antibody (HIV 1/2 type O Ab)
  - Anti-Human T cell lymphotropic Virus (HTLV) antibody (HTLV I/II Ab)
  - Rapid Plasma Reagen (RPR)
  - Cytomegalovirus antibody (CMV)
  - HCV/HIV Nucleic Acid Test

Additional tests shall be performed as required to assess the possibility of transmission of other infectious or non-infectious diseases.

**Prior to lymphocyte collection:** Within 72 Hours:

- 1) H&P, vital signs.
- 2) Albumin, total protein, calcium, glucose, BUN, Creatinine, bilirubin, ALT, Alkaline phosphatase, LDH, CBC with differential, PT/PTT.
- 3) Toxicity assessment.
- 4) Collect 10 cc serum and 60 cc whole blood in preservative-free heparin for idiotype-specific antibody and cellular proliferative responses.
- 5) Negative donor infectious disease panel:
  - Hepatitis B surface antigen (HBsAg)
  - Anti-Hepatitis B core antibody (HBcAb)
  - Anti-Hepatitis C Virus antibody (HCV Ab)
  - Anti-Human Immunodeficiency Virus (HIV) antibody (HIV 1/2 type O Ab)
  - Anti-Human T cell lymphotropic Virus (HTLV) antibody (HTLV I/II Ab)
  - Rapid Plasma Reagen (RPR)
  - Cytomegalovirus antibody (CMV)
  - HCV/HIV Nucleic Acid Test

Additional tests shall be performed as required to assess the possibility of transmission of other infectious or non-infectious diseases.

**B. Recipient:**

**Within 10 days prior to lymphocyte infusion and within 72 hours prior to each vaccine:**

- 1) H&P, vital signs.
- 2) Albumin, total protein, calcium, glucose, BUN, creatinine, bilirubin, ALT, alkaline phosphatase, LDH, CBC with differential, PT/PTT.
- 3) GVHD assessment.
- 4) Immunodeficiency panel.
- 5) Negative serum pregnancy test if of child bearing potential.
- 6) Disease specific assessment:
  - SPEP, UPEP, serum and immunofixation electrophoresis, serum for free kappa and lambda light chain assay, Beta 2 Microglobulin, and C reactive protein.

- 7) Collect 10 cc serum and 60 cc peripheral blood in preservative-free heparin for idiotype-specific antibody and cellular proliferative responses, immediately prior to donor lymphocyte infusion, 1 hour after the donor lymphocyte infusion.
- 8) Idiotype-specific humoral and cellular responses will be assessed in both donor and in the recipient post-transplantation.
- 9) Negative donor infectious disease panel:
  - Hepatitis B surface antigen (HBsAg)
  - Anti-Hepatitis B core antibody (HBcAb)
  - Anti-Hepatitis C Virus antibody (HCV Ab)
  - Anti-Human Immunodeficiency Virus (HIV) antibody (HIV 1/2 type O Ab)
  - Anti-Human T cell lymphotropic Virus (HTLV) antibody (HTLV I/II Ab)
  - Rapid Plasma Reagen (RPR)
  - Cytomegalovirus antibody (CMV)
  - HCV/HIV Nucleic Acid Test
  - West Nile Virus Nucleic Acid Test
  - Sickledex
  - T Cruzi AB

Additional tests shall be performed as required to assess the possibility of transmission of other infectious or non-infectious diseases.

### **C. Donor Long-Term Follow-Up:**

#### **Procedures and Tests:**

Donors will have the following procedures and tests at 1, 12, and 24 ( $\pm$  1 week) post donor lymphocyte collection at MD Anderson Cancer Center if possible.

- 1) H&P, vital signs.
- 2) Albumin, total protein, calcium, glucose, BUN, creatinine, bilirubin, ALT, Alkaline phosphatase, LDH, CBC with differential, PT/PTT.
- 3) Immunodeficiency panel.

If the donor is not able to return to MD Anderson Cancer Center for long-term follow-up, the donor should have the procedures and tests performed with a local physician, as approved by the Study Chair. The results should be sent to research staff at MD Anderson Cancer Center.

#### **Telephone Follow-Up:**

Donors will receive a telephone follow-up call once a year for 5 years, starting at month 24 ( $\pm$  1 week) post donor lymphocyte infusions. The telephone follow up will include questions regarding interim history, hospitalizations, new medications, and new allergies.

### **D. Recipient Long-Term Follow-Up:**

#### **Procedures and Tests:**

Recipients will have the following procedures and tests at 3, 6, 12, 18, and 24 months post last vaccine ( $\pm$  1 week)

- 1) H&P, vital signs.
- 2) Albumin, total protein, calcium, glucose, BUN, creatinine, bilirubin, ALT, alkaline phosphatase, LDH, CBC with differential, PT/PTT.
- 3) GVHD assessment.
- 4) Immunodeficiency panel
- 5) Disease specific assessment:
  - SPEP, UPEP, serum and immunofixation electrophoresis, serum for free kappa and lambda light chain assay, Beta 2 Microglobulin, and C reactive protein.

-Bone marrow aspiration and biopsy for cytogenetics, chimerism, and myeloma panel: Kappa, Lambda, CD138 staining.

6) Collect 10 cc serum and 60 cc peripheral blood in preservative-free heparin for idiotype-specific antibody and cellular proliferative responses, immediately prior to donor lymphocyte infusion, and months ( $\pm$  1 week) 1, 2, 3, 4, 6, 12, 18 and 24.

7) Idiotype-specific humoral and cellular responses will be assessed in both donor and in the recipient post-transplantation.

If the recipient is not able to return to MD Anderson Cancer Center for long-term follow-up, the recipient should have the procedures and tests performed with a local physician, as approved by the Study Chair. The results should be sent to research staff at MD Anderson Cancer Center.

**Telephone Follow-Up:**

Recipients will receive a telephone follow-up call once a year for 5 years, starting at month 24 ( $\pm$  1 week) post donor lymphocyte infusions. The telephone follow up will include questions regarding interim history, hospitalizations, new medications, and new allergies.

**OPTIONAL PROCEDURE**

Recipients will be asked for permission to obtain additional blood samples for future testing as well as a punch skin biopsy using standard techniques in an area around the vaccination to identify types of cellular infiltrates.

Unused cells or vaccines generated for this study which are not infused into the recipients will be used for research purposes.

**E. Evaluation of Toxicity and Data Collection (Donors and Recipients)**

The severity of the adverse events observed in the proposed treatment will be graded according to the Common Terminology Criteria v3.0 (CTCAE).

Events not included in the CTCAE chart will be scored as follow:

General grading:

Grade 1: Mild: discomfort present with no disruption of daily activity, no treatment required beyond prophylaxis.

Grade 2: Moderated: discomfort present with some disruption of daily activity, require treatment.

Grade 3: Severe: discomfort that interrupts normal daily activity, no responding to first line treatment.

Grade 4: Life Threatening: discomfort that represents immediate risk of death.

Expected adverse events (AEs) related to the vaccine injection :

1. Local reactions (erythema, induration, swelling and tenderness),
2. Fever, chills,
3. Rash,
4. Myalgias and arthralgias.
5. Mild elevations in creatinine phosphokinase (CPK).

Expected adverse events (AEs) related to GM-CSF:

1. Fever, chills, diaphoresis
2. Myalgias, fatigue, malaise
3. Headache, dizziness
4. Dyspnea, bronchospasm, pleural effusion
5. Anorexia, indigestion, nausea, vomiting, diarrhea

6. Urticaria, rash, pruritus, hypersensitivity reactions
7. Bone pain
8. Thromboembolic events, phlebitis
9. Hypotension
10. Peripheral edema
11. Leukocytosis, thrombocytosis or thrombocytopenia
12. Hepatic enzyme abnormalities and bilirubin elevation have been recorded.

Expected adverse events (AEs) related to the vaccine:

1. Autoimmune reactions (hypogammaglobulinemia, collagen vascular diseases, cytopenias).
2. Local reactions

Expected adverse events (AEs) related to the DLI:

1. Graft versus host disease

#### **Casualty Assessment:**

For the purpose of this study adverse events known to be caused by the vaccine administration, GM-CSF, donor lymphocyte infusion and to the vaccine and its direct consequences will be scored as definitive related.

Adverse events known to be related to drugs used for the treatment of Medical problems arise as direct consequences of known adverse events will be scored as probable related.

When the relationship of the adverse event cannot be ruled out with certainty the AE may be considered possible related.

